Professor of Old Age Psychiatry, Newcastle University and Honorary Consultant at Gateshead Health NHS Foundation Trust

[contact]

[name]

Senior Clinical Lecturer, Newcastle University

[contact]

[name]

Professor of Old Age Psychiatry, Newcastle University

[contact]

[name]

Group Director for Planned Care, Northumberland Tyne and Wear NHS Foundation Trust

[contact]

[name]

Trial Statistician, Newcastle University

[contact]

[name]

Lay Member and Consumer Representative

[contact]

[name]

Clinical Senior Lecturer and Consultant in Geriatric Medicine,
Newcastle University

[contact]

[name]

Senior Research Associate, Newcastle University

[contact]

[name]

Senior Lecturer, Newcastle University

[contact]

[name]

Professor of Health Economics, University of Warwick

[contact]

[name]

Health Foundation Chair in Health Economics, Newcastle
University

[contact]

TRIAL SUMMARY

Trial Title	Work Package 5A and 5B A pilot cluster randomised study of the management toolkit in NHS secondary care services.
Acronym	DIAMOND-Lewy Work Package 5
Summary of Trial Design	Pilot, cluster randomised controlled trial (cRCT)
Summary of Participant Population	
A: Patients referred for assessment and diagnosis of memory problems to dementia/memory assessment services, aged 60 and over and their carers
 
B: Patients aged 60 and over, diagnosed with Parkinson’s disease and their carers.

Planned Sample Size	
A: 60 patients entered into the cRCT & their carers
 
B: 60 patients entered into the cRCT & their carers
 
Total Sample size: 240 participants (patients + carers)

Planned Number of Sites	
8 services
 
A: Memory assessment services (Dementia with Lewy Bodies)
 
B: Neurology and geriatric services (Parkinson’s Disease Dementia)

Intervention	Management Toolkit for neurodegenerative dementia of Lewy body type
Follow Up Duration	6 months
Planned Trial Period	3 years
Main Objectives	
 • Determine feasibility of use of the intervention • Assess the impact of the assessment and management toolkit on patient management, health outcomes, and its impact on informants/carers • Provide an exploratory comparison of the cost-effectiveness of the new assessment and management toolkit for LBD with usual care

Contents

RESEARCH REFERENCE NUMBERS	2
SIGNATURE PAGE	3
KEY TRIAL CONTACTS.....	4
TRIAL SUMMARY	7
GLOSSARY OF ABBREVIATIONS.....	9
1. BACKGROUND	12
2. RATIONALE	13

PIC	Participant Identification Centre
PIS	Participant Information Sheet
QA	Quality Assurance
QALYs	Quality Adjusted Life Years
QC	Quality Control
QoL	Quality of Life
PDD	Parkinson's Disease Dementia
R&D	Research & Development
RCT	Randomised Control Trial

REC	Research Ethics Committee
RUD	Resource Utilisation in Dementia instrument
WP	Work Package

1. BACKGROUND

The accurate recognition of dementia, the diagnosis of subtypes of dementia and ensuring appropriate management are central to improving the care of patients with dementia. There is evidence that accurate diagnosis reduces levels of depression and anxiety, and improves quality of life (QoL), both of people receiving a diagnosis and their carers/informants.

Dementia with Lewy Bodies (DLB) is a type of dementia that shares symptoms with both Alzheimer's disease (AD) and Parkinson's disease (PD). DLB is the second most common cause of dementia in older people after AD. **Parkinson's Disease Dementia (PDD)** occurs when a patient with Parkinson's disease develops progressive dementia. Longitudinal studies show that PDD develops in up to 80% of people with Parkinson's.

PDD and DLB together are known as **Lewy Body Dementia (LBD)** as they share common clinical features, have closely overlapping neurobiology and respond to similar approaches to management. Lewy bodies are small deposits of protein found in nerve cells. Their presence is linked to a loss of connection between nerve cells, and over time there is a progressive death of nerve cells and loss of brain tissue. The loss of these cells causes dementia, but it is not yet understood why or how Lewy bodies occur in the brain. LBD accounts for 15-20% of all dementia cases, affecting between 160,000 and 200,000 people in the UK. It is expected that this prevalence will approximately double over the next 30 years, and therefore, LBD represents an important disease affecting a growing proportion of the population.

Currently, even in specialist hospital services, there is evidence of under recognition and inappropriate management of people affected by LBD. This is because the signs and symptoms of LBD, such as visual hallucinations, variability in memory and changes in sleep are very hard to detect. Improved diagnosis of LBD may be facilitated by the introduction of an assessment tool into routine practice which systematically explores these symptoms. Inappropriate management, when LBD is not recognised, could include use of antipsychotic agents which can have serious adverse reactions in LBD subjects, and the failure to recognise and manage distressing symptoms such as sleep disorder and autonomic features.

2. RATIONALE

2.1 The need to improve the recognition and management of DLB

Current evidence indicates that only around 1 in 3 cases of DLB are currently detected, with the other 2 either not detected or misdiagnosed (usually with Alzheimer's disease). The Galvin study (J.E Galvin et al 2010) showed almost 80% of DLB cases were initially given a non DLB diagnosis, with half receiving more than 10 clinic visits before the correct diagnosis was made. For those patients recognised as having DLB, the management care pathways are poorly developed in comparison with AD.

Some of the key reasons for the difficulties in recognising, diagnosing and appropriately managing patients with DLB include:

- 1) A lack of assessment of key clinical symptoms such as visual hallucinations, slowness of movement and sleep disorder in dementia assessment services.
- 2) A lack of knowledge among clinicians regarding the management of DLB in comparison to the other two main and better established causes of dementia; AD and vascular dementia.
- 3) Delays in translating recent advances in DLB management into NHS care.

There is a particular danger that patients who have not been diagnosed with DLB could be prescribed antipsychotics due to their high prevalence of psychotic symptoms. Prescriptions of these are contra-indicated in DLB because of potential catastrophic sensitivity to these drugs and increased mortality. This highlights the importance of disease specific information and management.

2.2 The need to improve the recognition and management of PDD

Patients with PD are often reviewed regularly in neurology or geriatric medicine services, but there are still problems in recognising and diagnosing PDD. Only around 1 in 3 of those with PDD are currently recognised and diagnosed, and this often occurs late in the disease.

Some of the key reasons for the difficulties in recognising, diagnosing and appropriately managing patients with PDD include:

- 1) Cognitive impairment develops insidiously and at a variable time after PD diagnosis.
- 2) Initial symptoms such as fluctuation, attentional problems and visual hallucinations may be thought to be related to medication side effects.

2.3 The need to improve the recognition and management of LBD (DLB and PDD)

When dementia is recognised there are effective pharmacological and non-pharmacological strategies for cognitive symptoms, psychosis, sleep disturbance and other psychiatric problems. The recognition of dementia allows the provision of support, education and advice, access to services, financial and other benefits and opportunities for future planning and attending to medico-legal issues. This improves long term outcome in terms of reducing carer stress and delaying the need for care.

There is a clear need to improve the assessment, diagnosis and management of LBD both in memory/dementia services and movement disorder services. There is currently no single, simple tool which incorporates the range of clinical symptoms for LBD, and there is no unified evidence based management care pathway. This study is looking to develop a management toolkit for routine use in patients with DLB and PDD in NHS services.

2.1. Work Packages

This overall work programme is aiming to improve the NHS care of people with dementia by increasing detection and optimising management of LBD in routine secondary care services. In order to achieve this there are a total of 5 related work packages. Although this protocol refers to Work Package 5, the other four work packages are also briefly outlined below.

Work Package 1 (WP1): This was a baseline study of current Lewy Body Dementia (LBD) diagnosis and management in memory, neurological and medical services. The proportion of cases diagnosed with DLB and PDD and their management pathways were compared to non-DLB dementia cases and PD cases without dementia, respectively.

Work Package 2 (WP2): This was a series of qualitative studies to explore and understand perceived barriers and facilitators to introducing an assessment tool and management toolkit into routine NHS practice. It examined current practice through observing clinic consultations, and conducting interviews with professionals, patients and carers.

Work Package 3 (WP3): This study involved developing an evidence based management toolkit to guide clinicians in the management of LBD. A systematic review of existing evidence was conducted and guided using a Delphi panel approach of a group of expert clinicians and PPI members.

Work Package 4 (WP4): This study brought together previously validated assessment methods into a simple LBD assessment tool suitable to use in the NHS. The assessment tool and previously developed

management toolkit were piloted in Gateshead NHS Trust. Modifications to the tools were made following feedback from staff, patients and carers.

Work Package 5 (WP5): This study involves introducing the management toolkit into routine NHS care in a minimum of 8 different services. A pilot cluster randomised controlled trial (cRCT) will be conducted to test the management toolkit. WP5A will focus on DLB and will run in memory assessment services. WP5B will focus on PDD and will run in movement disorder (neurology and geriatric) services. **This is the focus of this protocol.**

2.2. Risk Assessment

Low risk to patients: Participating services will be randomised to use either the management toolkit or usual management care. The management toolkit provides recommended guidelines to be used by clinicians as part of their clinical patient management. The toolkit does not recommend any treatments or assessments that are not already used in the NHS.

3. AIMS, OBJECTIVES AND OUTCOME MEASURES

3.1. Aims and Objectives

The overall aim of the programme is firstly to improve the recognition and prompt diagnosis of LBD in routine NHS secondary services using a simple clinical tool for assessment of key symptoms. Secondly, for clinicians to improve patient management after diagnosis using an evidence based management toolkit.

Work package 5 will conduct a pilot cluster randomised controlled trial (cRCT) to test the management toolkit. It will look to:

- Determine feasibility of use of the intervention
- Assess the impact of the management toolkit on patient management, health outcomes and impact on carers/informants
- Provide an exploratory comparison of the cost-effectiveness of the new assessment and management toolkit for LBD with usual care

The cRCT will provide data on impact on patient symptoms, outcomes, quality of life and informant/carer stress (quality of life). It will provide data on rates of consent and drop out, as well as suitability of the outcome measures. It will also provide data on the use of the management toolkit by clinicians.

An exploratory health economic analysis will be conducted using data collected from WP1 and WP5 to estimate the overall cost effectiveness of implementing the new management toolkit in the NHS compared to usual care, as well as economic impact on the NHS, personal social services, informal carers and relatives.

Hypothesis:

We hypothesise that DLB and for PDD subjects treated in services randomised to implementing the management toolkit will result in symptom improvement, increased quality of life and decreased carer stress at 6 months compared to baseline.

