4. TRIAL DESIGN

A pilot cluster randomised controlled trial (cRCT) design will be used to test the management toolkit. Participating services will be cluster randomised with half implementing the management toolkit (intervention arm) and half implementing usual clinical care (control arm). The study team will disseminate the management toolkit to the clinical teams in the intervention arm and provide appropriate training. Clinicians will use the toolkit as part of their clinical management of LBD patients according to their clinical judgement.

The study will be discussed and consent taken from the patient (or consultee) and the carer/informant for the additional study visits and for data to be collected for the study. For both arms of the study an additional visit will be arranged to conduct a baseline visit, 3 month and 6 month follow up visits.

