7.7. Trial Assessments

Measurements will be conducted at 3 months (+2 weeks) and 6 months (+2 weeks) after the baseline visit as listed in table 1. The primary outcome for the study will be the 6 month assessment. If it is determined at the follow up visits that the patient is no longer able to complete the additional measurements, the visit may continue with the informant/carer providing information as a participant. The informant/carer does not need to be present at all follow up visits as some questions can be completed on the telephone.

[figure not shown]
Table 1.

	Baseline	3 Months	6 Months
Patient			
Consent	X		
MMSE	X	X	X
MoCA	X	X	X
GDS-15	X	X	X
UPDRS-III	X	X	X
DEMQOL	X	X	X

EQ-5D-5L	X	X	X
Carer/informant relating to patient			
Consent	X		
NPI	X	X	X
Cornell	X	X	X
BADL	X	X	X
DCFS-R	X	X	X
DEMqoL-Proxy	X	X	X
Proxy EQ-5D-5L	X	X	X
Baseline Global outcome scale (regarding patient)	X		
Global outcome (regarding patient)		X	X
Use of services and costs*	X	X	X
Time and travel questionnaire*			X
Carer/informant relating to themselves			
Zarit	X	X	X
EQ-5D-5L	X	X	X
HADS	X	X	X
Use of services and costs*	X	X	X
Time and travel questionnaire*			X
Researcher relating to patient			
Galvin Lewy Body Composite Score	X		X
Global Outcome Scale		X	X

*The same questionnaires will give the information of the services used, and time and travel needed for both the patient and the carer

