9.2. Statistical Analyses

Hypothesis

For the definitive trial we hypothesise that DLB and for PDD subjects treated in services randomised to implementing the management toolkit will result in symptom improvement (reduced neuropsychiatric inventory score, lower unified Parkinson's disease rating scale score, greater improvement in CGIC global and symptom ratings), increased quality of life (DEMQOL and DEMQOL-proxy scales) and decreased carer stress (HADS, Zarit burden scale) at 6 months compared to baseline. In this pilot study, we will conduct an exploratory analysis where we will rehearse the analysis proposal for the full trial.

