9.2.2. Statistical Analyses

As the management tool covers both DLB and PDD it will be appropriate to undertake exploratory analysis on the combined PDD and DLB subject group. As the hypothesis concerns changes in symptom scores between baseline and 6 months we will use T-tests in an exploratory analysis to compare the means of two samples when data is normally distributed and a Wilcoxon Signed test will be used to compare the medians of two samples when data is skewed. The association of a binary outcome with a categorical predictor with 2 or more levels will be tested using the Chi-square test. Further analysis involving the data measured at baseline, 3 months and 6 months will be done by using a linear mixed regression model to test for between group and between time differences.

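### The hypothesis is a change from baseline within toolkit services, and section 9.2.2 builds its tests on it without stating a toolkit-versus-usual-care contrast at 6 months

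*Protocol*

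**What the plan says.** Section 3.1 of the protocol states the hypothesis for "subjects treated in services randomised to implementing the management toolkit": the toolkit "will result in symptom improvement, increased quality of life and decreased carer stress at 6 months compared to baseline". Section 9.2 restates it for the definitive trial with named scales and the same ending, "decreased carer stress (HADS, Zarit burden scale) at 6 months compared to baseline". Neither statement names usual care as the comparator.

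Section 4 allocates half of the services to the toolkit and half to usual care. Section 7.7 fixes the time point: "The primary outcome for the study will be the 6 month assessment".

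Section 9.2.2 takes its tests from the hypothesis: "As the hypothesis concerns changes in symptom scores between baseline and 6 months we will use T-tests". The t-test compares two samples that are not identified. For skewed data the plan names a Wilcoxon Signed test. Section 9.2.1 gives the same pair of tests. A further analysis of baseline, 3-month and 6-month data uses a "linear mixed regression model to test for between group and between time differences". No arm contrast at 6 months is stated.

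On the status of these analyses, section 9.2 says "we will conduct an exploratory analysis where we will rehearse the analysis proposal for the full trial".

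**The concern.** A randomised trial answers its question by comparing arms. The stated hypothesis compares the toolkit arm with its own past, so the control arm plays no part in deciding whether it is met. Dementia is progressive, as the Background section describes for this disease. A change from baseline therefore mixes natural decline with any toolkit effect.

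Two errors could follow. A before-after test may be significant although the toolkit does nothing. A toolkit that slows decline may be judged a failure because scores still worsened. The wording also carries into the tests. The only skewed-data procedure named is a paired one, which fits two visits in the same patients and cannot compare two independent arms. Because the pilot rehearses the full-trial analysis, the same wording could pass into the definitive trial.

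**Working it through.** **Side by side**

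| Item | Comparison stated |
|---|---|
| Design (section 4) | toolkit services against usual-care services |
| Hypothesis (3.1, 9.2) | 6 months against baseline, toolkit services |
| t-test (9.2.1, 9.2.2) | two samples, not said whether arms or visits |
| Skewed-data test (9.2.1, 9.2.2) | signed test, so paired |
| Mixed model (9.2.2) | group differences and time differences over three visits |

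Only the first row is clearly a between-arm comparison at a defined level. None of the analysis rows names the arm contrast at 6 months.

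**Inputs.** Section 9.1 plans 30 patients per arm in each of WP5A and WP5B, so 30 + 30 = 60 per arm in the combined analysis. The protocol gives no SD, correlation or effect size, and the sample size is a rule of thumb, so there is no power figure to reproduce. The values below are assumptions in baseline SD units, with equal SDs at both visits. Clustering is ignored.

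**1. Before-after test when the toolkit does nothing**

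Let both arms change by c, with baseline to 6-month correlation r.
- SD of the change = √(2(1 − r)). With r = 0.6 this is √0.8 = 0.894.
- Noncentrality = c√n / SD. With c = 0.3 and n = 60 this is 0.3 × 7.746 / 0.894 = 2.60.
- Rejection probability at two-sided 5%: 0.72 for the paired t-test (noncentral t), and 0.71 for the signed-rank test by simulation (4,000 runs).
- A between-arm test of the same changes rejected 5% of the time in simulation.

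Range for the paired t-test in the toolkit arm:

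| c | n = 30, r = 0.5 / 0.7 | n = 60, r = 0.5 / 0.7 |
|---|---|---|
| 0.2 | 0.19 / 0.28 | 0.33 / 0.50 |
| 0.3 | 0.36 / 0.54 | 0.63 / 0.84 |
| 0.5 | 0.75 / 0.93 | 0.97 / >0.99 |

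If c is a decline, these are significant worsenings, not false claims of benefit.

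**2. A toolkit that slows decline.** Suppose usual care declines by 0.3 SD and toolkit services by 0.1 SD. The between-arm effect is 0.3 − 0.1 = 0.2 SD in favour of the toolkit. The toolkit arm is still 0.1 SD worse than at baseline, so the hypothesis as worded fails.

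**3. Mixed model, if it is additive.** With balanced data and baseline as an outcome visit, the group term is the mean of the three arm differences. Let the 6-month effect be 1 and the baseline difference 0:
- full effect by 3 months: (0 + 1 + 1)/3 = 0.67
- linear build-up: (0 + 0.5 + 1)/3 = 0.50
- effect only at 6 months: (0 + 0 + 1)/3 = 0.33

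A simulation with a true 6-month effect of 0.50 SD and linear build-up gave 0.25 for the additive group term and 0.49 for the arm-by-visit term at 6 months. The time term pools both arms and is not a treatment effect.

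These fractions require a zero effect at baseline. Section 7.1.1 concedes that the baseline visit may follow first use of the toolkit, so the premise may fail for some patients.

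**The case against.** The strongest reply is that a reader might infer that nothing in the plan compares the arms, and the text does not support that. A t-test on changes in a two-arm trial can fairly be read as comparing change scores between arms, which is a legitimate contrast. The mixed model tests group differences and so uses the control arm. Its description does not exclude an arm-by-visit term, and an analysis plan that is not shown may specify one. The objectives speak of the toolkit's impact, and the economic objective names usual care. All of this stands. The t-test and model limbs are therefore faults of unclear wording, not proof of a wrong analysis. It does not rescue the hypothesis, stated twice without a comparator, or the paired test named for skewed data.

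Adjusting for baseline rather than analysing change scores is largely a matter of efficiency. At correlation 0.5 / 0.6 / 0.7 the variance ratio (1 − r²)/(2(1 − r)) is 0.75 / 0.80 / 0.85. That is a reason to prefer adjustment, not an error in the plan.

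A reader might also infer that regression to the mean would create apparent benefit, because recruits have an active clinical issue. That criterion applies to WP5A only, is judged by the treating team, and does not imply a high score on any particular scale. No figure for it is supportable.

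Finally, section 9.3 concedes that the sample may be too small to test the hypothesis, and no decision rule hangs on these p-values. That lowers the severity.

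**Conclusion.** The concern holds at moderate severity. The firm part is the hypothesis in 3.1 and 9.2, which leaves out usual care and conflicts with the randomised design, together with the paired test that follows from it. The unidentified samples and the incomplete description of the mixed model need clarifying.

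Followed as a before-after test, the plan would reject about 70% of the time with no toolkit effect, under an assumed 0.3 SD decline, correlation 0.6 and 60 patients. That rejection would be in the direction of worsening. The 50% to 67% recovery by the group term is doubly conditional: on an additive model, and on a baseline taken before toolkit use.

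It would go too far to conclude that the pilot will yield a false efficacy claim, since its analyses are declared exploratory. The reason to act is that they rehearse the definitive trial.

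**What to change.** - **3.1 and 9.2:** reword the hypothesis so that the comparison at 6 months is with usual-care services.
- **9.2.1 and 9.2.2:** replace the paired signed test with a between-arm comparison, and say that the two samples are the two arms.
- **9.2.2:** state the estimate as the arm contrast at 6 months with a 95% CI. Take it from a mixed model of the 3- and 6-month scores with arm, visit, arm-by-visit and baseline score as fixed effects, and random effects for service and participant.
- **Baseline timing:** because 7.1.1 allows a baseline visit after first toolkit use, report that timing and add a sensitivity analysis without baseline adjustment.

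The cost is modest. The outcome scores needed are already collected at all three visits. The model is re-specified rather than merely reworded, and there is one extra analysis. The date of first toolkit use is not among the items listed in 7.6 or Table 1, so it may have to come from clinical records. Where baseline is late, adjusting for it may remove part of the toolkit effect, which the sensitivity analysis is there to show.
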